## **Study Visit Procedures**

### **AIM 1**

In Phase 1 (Aim 1), interested WHLA, Peer Navigators, and Key Informants will participate in one focus group or in-depth interview, lasting approximately 90-120 minutes. All FGs will be held at the UCSD research field office location in Hillcrest (The Webster Building), a centrally located neighborhood in San Diego. Key Informant Interviews will occur at a location convenient for the key informant, such as their office. Each session will last approximately 2 hours and will be conducted in English. Participants will be asked to review and sign the informed consent form, which will explain the study procedures, confidentiality, risks and benefits of participation, and payment incentives. Participants will be given the opportunity to ask questions about interview procedures, and “group rules” will be reviewed prior to beginning the session (in the case of the FGs). To ensure confidentiality, participants will be asked to use a pseudonym in lieu of their name.

Participants will also be asked to sign a confidentiality clause and encouraged to use and refer to each other by pseudonym only. FG and key informant interview questions will be developed by the research team and reviewed by the CAB. Questions specific to smartphones and apps will include: (1) experiences with smartphones and apps; (2) important features in an app; (3) influences of decisions to download, use, and maintain apps; features desired in regularly used apps; (4) suggestions for content and features of an app to help engage women in HIV medical care and ancillary support services; (5) prompts provided based on proposed app components: video function, social networking, educational tips, and GPS-based locator service.

Topics and questions specific to HIV care, interpersonal violence, and associated mental illness and/or substance abuse will include: (1) aspects of HIV care most challenging to navigate as Black WLHA; (2) how barriers have been overcome, such as interpersonal violence, leading to improved engagement in HIV care or

other support services; (3) intersectional stigma due to being Black, a woman, HIV-positive, and affected by interpersonal violence, and distrust of the health care system; (4) type of appointments that clients would need support in; and (5) types of support needed after appointments (e.g., managing medication side effects). Next, participants will be informed that the research team is building a smartphone app to improve retention in HIV medical care and ART adherence, while linking to other ancillary support services (e.g., domestic violence, mental health, substance abuse). Participants will be asked to reflect on the following topics: (1) features and functions that would attract them to the app; (2) visual look of the app; (3) importance of photos or characters of people on app look like them or their friends; (4) thoughts on proposed name, LinkPositively and suggested changes; (5) feedback on notifications (usually called push notifications) that may pop up on the home screen or near the app; and (6) suggestions to address privacy and safety concerns. The FG or key informant interview will end by asking participants to comment on anything else to consider during the app development process, thanking them for their time, and compensating them \$50 cash.

In Phase 1 (Aim 1), we will conduct beta testing to obtain feedback from a small group of women on intervention components, and to identify any navigation problems. Beta testing will be informed by the Health and Human Services Agency guidelines for best practices to assess user reaction to content, design, and functionality of the LinkPositively app. Screening and written informed consent will be conducted in-person. The consent will describe the purpose of usability testing and a description of the LinkPositively app to be tested. Women will be asked to download and navigate the LinkPositively app and reflect upon their experiences over a 2-week period. Specifically, we will ask women to provide feedback on their experiences with: 1) completion of a profile to be effectively linked to a matched virtual PN; 2) ease of initial text or videoconference with virtual PN; 3) use and functionality of the social networking platform with other users; 4) use of the resource center to identify one HIV service provider or organization, outside of the clinic or organization they frequent, and 2 ancillary support service agencies (i.e., domestic violence, mental health, substance abuse), and 5) educational tip functionality in terms of receiving tips and submitting questions.

At the end of two weeks, [name] or [name] will conduct a semi-structured qualitative exit interview soliciting participant and Virtual PN feedback and suggestions specific to each intervention feature, noting suggestions for improvement. Participants will be asked to assess the LinkPositively app's features usability, design, content, and functionality. Participants will also complete the 10-item system usability scale (SUS), a validated, industry standard scale used to evaluate a variety of products and services, including websites, mobile phones, and computer software. Virtual PNs will also participate in a FG where we will obtain feedback on navigating the Coach-User interface (e.g., video and phone feature to speak with women, texting appointment reminders and private messages to women), difficulties with session content, satisfaction with the process (e.g., linkage to external support services, support networks, match between PN and client), and suggestions for improvements. Upon completion of a qualitative exit interview, participants will receive \$50 for their participation and to cover the cost of data used during beta testing. A usability report will include compiled data from participants and PNs, list of common problems, and recommended design-improvements that will be used in the final iterative stages of app development.

After beta testing is completed, we will share findings with the CAB and improve the LinkPositively app design, content, and functionality based on findings from the usability testing process. Drs. [name] and [name] will meet with RCG to discuss refinements centered on the identified usability study findings.

## AIM 2

In Phase 2 (Aim 2), Participants enrolled in the study will attend three data collection study visits: Baseline (Month 0), Follow-Up 1 (Month 3), and Follow-Up 2 (Month 6).

**Baseline Study Visit.** Women who meet eligibility criteria and are interested in participating in the study will undergo the written informed consent process at their baseline visit. After consenting, participants will provide contact information (e.g., name, cell phone number, email address, and/or social media username) to be

contacted for follow-up assessments. Informed consent, completion enrollment paperwork, and assessments will occur in field offices in San Diego County (UC San Diego AntiViral Research Center, located at [name]), Los Angeles County (Charles R. Drew University of Medicine and Science, Clinical and Translational Science Institute, [name]), Alameda County (WORLD, located at [name]), Oklahoma City (Guiding Right Offices, [name], [name], and [name]) and Tulsa County (Guiding Right, Inc., [name]). Following the baseline visit, participants will be randomized using a randomization sequence at a 1:1 ratio into the intervention or control arm on a rolling basis.

**All Study Visits.** At all study visits (Baseline, Follow-Up 1, Follow-Up 2), participants will undergo an interviewer-administered quantitative survey and biological sample collection (hair). An increasing payment schedule will be used to enhance motivation to complete surveys. Specifically, women will receive \$25 for completing the baseline visit, \$30 for completing the 3-month follow-up visit, and \$40 for completing the 6-month follow-up visit, with a \$10 bonus for completing all 3 visits. Due to the ongoing COVID-19 pandemic, follow-up study visits may occur virtually, over the secure video conference platform Zoom. For all in-person study activities, participants and staff will be required to wear face masks and physically distance when feasible. If participants do not have access to a face mask, one will be provided to them upon entry to the private research office space. Additionally, all participants will be screened for symptoms of COVID-19 by the Research Associate one day in advance of all in-person study visits, and again upon arrival at the private research office space.

**Quantitative Survey.** The quantitative survey will include the following sections: (1) Demographic questions (e.g. age, biological sex at birth, gender identity, race/ethnicity, education, sexual orientation, marital status, employment, number of children, housing status, medical insurance status, food insecurity); (2) Socioeconomic status; (3) Mental health and behavioral health history (e.g. depression, anxiety, alcohol and substance use diagnosis and/or abstinence, lifetime history of trauma); (4) HIV care and treatment history (e.g. obtaining medical care, usual source of medical care, treatments, medications, insurance status, barriers to HIV treatment, self-reported adherence, adherence self-efficacy); (5) Support and Coping (e.g. social support, coping self-efficacy, ancillary support utilization); (6) Health care interactions (e.g. HIV stigma, medical mistrust) (7) Syndemic factors (e.g. interpersonal violence). [See Quantitative Survey].

**Biological Sample Collection.** After completion of the interviewer-administered survey at baseline, 3- and 6-month follow-up, the Project Coordinator or Research Associate (trained in hair sample collection by [name]) will retrieve a hair sample from participants. All participants will be compensated \$25 per visit, upon completion of hair sample collection. The hair sample collection kit is comprised of scissors, piece of tin foil, two patient labels, plastic (e.g., Ziploc) bag, alcohol swabs, and desiccant pellet. The following steps will be followed for hair sample collection: (1) Clean the blades of a pair of scissors with an alcohol pad; (2) Lift up the top layer of hair from the occipital region of the scalp at the back of the participant's head. Isolate a small thatch of hair (~100 fibers of hair) from underneath this top layer; (3) Cut the small hair sample as close to the scalp as possible. For short or cropped hair, the Project Coordinator can let hair fall directly into the piece of tin foil. For braided hair, cut hair thatch from in-between braids or dread locks; (4) Keep fingers on the part of the hair that was furthest away from the scalp and put the hair sample down on an unfolded piece of tin foil; (5) Put a thin label over the end of the hair sample that was furthest away from the scalp; (6) Refold the foil over to completely enclose the hair and place a study ID label on the folded piece of foil; (7) Place the folded piece of foil inside the plastic bag and seal the bag. Hair samples will then be securely mailed to the UCSF Hair Analytical Laboratory, led by [name], where liquid chromatography/tandem mass spectrometry will be used to assess antiretroviral concentrations in hair samples over the past 3 months (3cm of hair). Given the ongoing COVID-19 epidemic, all participants will also be trained in hair self-collection at their first (baseline) visit, and given labeled kits for self-collection of hair samples at home should the participant's follow-up visit occur virtually. If the follow-up visits occur virtually, study staff will arrange a date and time to pick up the hair samples at a location convenient and safe for the participant, shortly after the virtual study visit.

### **Medical Record Chart Abstraction**

During the passive follow-up period (7-12 months post-baseline), the research team will utilize the signed Release of Information (ROI) forms and HIPAA Authorization Forms of all study participants (participant consent collected at Baseline Study Visit), in order to request medical chart data for all participants from local HIV care providers to obtain data on clinic visits, HIV viral load, and CD4 values. Data will be entered into the REDCap Electronic Data Capturing System. These medical chart data extractions will be conducted periodically, given the staggered enrollment period.

To safeguard confidentiality, for the quantitative data collection, each participant will receive a unique patient identification number (PID) and names will never be used in conjunction with PID numbers. This unique PID number will appear on the survey, tracking forms (e.g., scrip payment receipt, cell phone tracking form), locator and screening forms. Participant confidentiality will be maintained through use of the unique PID and secure networks where data are stored. All laboratory data will be electronically transferred to the UCSD Data Management Center via password protected electronic files. At the UCSD Data Management Center, all computer files will be identifiable only by the PID number.

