##### **Aim 2: Conduct a pilot randomized controlled trial to assess the feasibility, acceptability and preliminary impact of the *LinkPositively* intervention for Black WLHA affected by interpersonal violence, in preparation for a large-scale R01.**

Eighty Black WLHA ever experiencing interpersonal violence will be randomly assigned (1:1) to receive *LinkPositively* or standard of care Ryan White services, with self-reported, biological, and clinical outcomes collected at baseline, 3- and 6-month follow-up visits. Intervention use data will be collected throughout the intervention period to examine feasibility, acceptability, and the associations between components used and study outcomes. Primary outcomes are retention in HIV care, ART adherence, and viral suppression, whereas socio-structural mechanism of change variables are social support and

activation of social support networks, self-efficacy, and utilization of ancillary support services. To minimize recall bias and/or social desirability bias, that may occur with the use of audio computer-assisted self-interviews, we will use objective data to measure the main outcomes. Retention in HIV care and viral suppression will be based on medical record data and ART adherence will be measured using hair samples assayed for tenofovir and emtricitabine. The proposed study will benefit the advancement of HIV prevention science by harnessing mobile technology to promote retention in HIV care and ART adherence among US Black WLHA affected by interpersonal violence and co-occurring adverse mental health and substance abuse – an underserved, marginalized population. If the LinkPositively intervention is efficacious through an eventual R01 mechanism, it will change the paradigm for addressing the unique HIV treatment needs for Black women dually affected by HIV and interpersonal violence.

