#### **AIM 2**

In Phase 2 (Aim 2), eligible participants for the RCT will self-report: (a) female gender (including transgender women), (b) Black or African American racial/ethnic background, (c) aged 18 years or older, (d) HIV-positive status, (e) ever experienced physical, sexual, and/or psychological abuse by a current or former partner or non-partner (e.g., relative, friend, stranger), (f) owner of a smartphone with internet browsing capabilities, and (g) English speaking. Purposive sampling will be used to ensure that groups are balanced with respect to type of perpetrator (current or former intimate partners [e.g., spouse, boyfriend, dating, casual] and non- intimate partners [e.g., family member, friend, stranger]) and retention in HIV medical care status (linked to care but have fallen out of care [i.e., no ART prescription filled, no viral load labs, or no HIV care visits with an ART-prescribing provider in the past year] versus linked to and retained in care [i.e., ART prescription filled, viral load labs, or HIV care visits with an ART prescribing provider in the past year]).

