## Statistical Analysis Plan

The statistical plan includes measuring feasibility of delivering the intervention, the acceptability of the LinkPositively intervention, and the impact of the intervention.

**Feasibility** The first step in assessing feasibility of delivering the intervention was by creating a Consort flow diagram tracking screening, eligibility, decision to participate, participation at baseline, and participation at 3-month and 6-month follow-ups. The second step in assessing feasibility was to compute the percentage of participants at baseline who were retained at 3-month follow-up and 6-month follow-up, and comparing proportion trends between the intervention and control groups. We used the following retention cut-off percentages to assess feasibility: a) 90+% = strong feasibility; b) 80-89% = acceptable feasibility; c) 70-79% = modest feasibility with a need for improvement; d) <70% = unacceptable.

**Acceptability** We assessed acceptability of the intervention by asking participants in the LinkPositively group about: 1) the quality rating of the program/app, 2) whether or not they received the type of program/app they were anticipating, 3) to what extent the program/app met their needs, 4) whether or not they would recommend the program/app, 5) level of satisfaction with the help received; 6) whether or not the program helped them deal more effectively with their problems, 7) level of satisfaction with the program received, and 8) whether or not they would seek help from the program/app again.

These measures of acceptability were assessed at both 3-month and 6-month follow-ups. At each timepoint, we computed mean scores and standard deviations, as well as median scores and interquartile ranges, for all continuous variables. We calculated frequency and percentages for all categorical variables.

**Intervention Impact** To estimate the preliminary effect of the intervention on primary outcomes we examined differences by group (intervention vs control) in responses to HIV care outcomes over time, ART adherence over time, and mental health outcomes over time. Responses were collected at baseline, 3-month follow-up, and 6-month follow-up. Due to the small n's, we calculated median scores and interquartile ranges for all continuous variables, and frequency/percentages for categorical variables. These statistics were stratified by group, and trends were compared, but significance could not be calculated due to low power.

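### Chart-based retention and viral suppression are promised at baseline, 3 and 6 months, but the abstraction states no record window, omits ART fills, and feeds an unadjusted comparison of arms

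*Combined protocol and SAP*

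**What the plan says.** Section 6 (Specific Aims, Aim 2) sets the outcomes and their sources: "Primary outcomes are retention in HIV care, ART adherence, and viral suppression". It adds that "Retention in HIV care and viral suppression will be based on medical record data", while "ART adherence will be measured using hair samples assayed for tenofovir and emtricitabine". The trial is to run "with self-reported, biological, and clinical outcomes collected at baseline, 3- and 6-month follow-up visits". The section prefers objective measures because self-report is open to recall and social desirability bias.

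Section 9, Medical Record Chart Abstraction, is the only place that describes how charts are obtained. In a passive follow-up period, 7 to 12 months after baseline, staff will "request medical chart data for all participants from local HIV care providers to obtain data on clinic visits, HIV viral load, and CD4 values". Release forms are signed at the baseline visit. No start or end date for the records is given.

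Section 9, All Study Visits, lists a survey and a hair sample at each visit; no blood draw or viral load test is mentioned.

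Sections 9 and 10 (Aim 2) call a woman out of care if she has "no ART prescription filled, no viral load labs, or no HIV care visits with an ART-prescribing provider in the past year", and use this status in purposive sampling so that groups are balanced. The source of the status is not named.

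The SAP (Intervention Impact) states: "Responses were collected at baseline, 3-month follow-up, and 6-month follow-up". It then gives medians or percentages by arm and compares trends, without adjustment, intervals or tests.

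**The concern.** Retention can only be observed over a period, so a baseline value needs a stretch of record before enrolment. Baseline suppression needs a dated viral load at or before entry. Neither is specified. The same gap affects months 3 and 6: no rule links a dated visit or laboratory result to either timepoint. Without a stated window, providers across five counties may return records covering different periods.

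The sample deliberately mixes women in and out of care, so status at entry is likely to be a strong predictor of status at month 6. If baseline chart values are absent or inconsistently defined, a chance gap between arms at entry can pass for an intervention trend. Women already suppressed also cannot be told apart from women who became suppressed. A descriptive SAP gives the reader little protection against either error.

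**Working it through.** **Text check**

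1. Outcomes that depend on the chart: 2 of 3 (Section 6, Aim 2). Adherence has its own baseline, because hair is collected at all three visits.
2. Alternative source for those two outcomes at study visits: none named.
3. Record window in the abstraction section: none. Chart definition of baseline, month 3 or month 6 in the SAP: none.
4. Markers of entry care status: ART fill, viral load laboratory test, HIV care visit. Items abstracted: visits, viral load, CD4. Fills are the missing marker.
5. Source of entry care status: self-report is stated for eligibility items (a) to (g), and care status is not one of them. The screener items listed do not include it. The baseline survey covers HIV care and treatment history (Section 9, Quantitative Survey), and charts are requested only months after randomization. The survey is therefore the only evident pre-randomization source, but this is an inference.

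**Size of a chance baseline gap**

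The plan has no figure of its own to reproduce: the 80 women carry no alpha, power or effect size. Inputs are 80/2 = 40 per arm, and 49% suppressed and 56% retained from Section 7. I assume that those background rates apply here and that allocation is not balanced on care status.

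- SE of the arm difference = sqrt(2p(1-p)/n). At p = 0.49: sqrt(2 × 0.49 × 0.51 / 40) = 0.112. At p = 0.56: sqrt(2 × 0.56 × 0.44 / 40) = 0.111. The 95% range is 1.96 × SE, about ±22 points for both.
- Ten points is 4 women of 40 and twenty points is 8 women. Exact binomial, two independent arms:

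| Baseline rate | Gap of at least 10 points | Gap of at least 20 points |
|---|---|---|
| 49% suppressed | 0.434 | 0.093 |
| 56% retained | 0.431 | 0.091 |

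A normal approximation without continuity correction gives about 37% for the 10-point gap. With the correction at p = 0.49 it is 3.5/40 = 0.0875, then 0.0875/0.112 = 0.78, a two-sided probability of about 0.43, which agrees with the exact figure.

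**What adjustment would gain**

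Assume no true effect, 49% suppressed at both times, and a baseline-to-month-6 correlation r. The SD of the adjusted difference is about 11.2 × sqrt(1 - r²) points:

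- r = 0.5: 11.2 × 0.866 = 9.7
- r = 0.7: 11.2 × 0.714 = 8.0
- r = 0.9: 11.2 × 0.436 = 4.9

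Simulation of 20,000 trials agrees (9.7, 8.0 and 4.9 against about 11 unadjusted). This needs a baseline value for every woman. If half had none, unrelated to suppression, and a missing category were used, simulation gives about 10.6, 9.8 and 8.6.

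**What an unseen gap does**

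Under the same assumptions the expected month-6 gap is r times the baseline gap. A 10-point baseline gap would leave 5, 7 or 9 points at month 6 with no effect of the intervention.

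**The case against.** Months 7-12 is when charts are requested, not the period that the records cover. The request has to look backwards anyway to supply month-3 and month-6 values, and Section 6 and the SAP both name a baseline. A reader might infer that no chart baseline will exist. The documents do not support that: one is promised but left undefined.

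A reader might also infer that entry care status is self-reported. That is plausible, but no source is stated and the survey instrument is not shown. Nor does the missing ART fill item create the baseline gap. Neither chart-based outcome is stated to depend on prescriptions, and adherence is measured in hair, which at baseline is itself an objective record of the prior three months' exposure. The omission only limits how fully entry care status can be checked from the chart, where two of the three markers are already abstracted.

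Purposive sampling is meant to balance groups on care status. If groups means arms and the balancing works, the 43% and 9% overstate the risk for retention. The text does not say how this would be done, and the randomization is described only as a 1:1 sequence.

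Finally, under the protocol's own definition, out-of-care women may have no viral load test in the past year. A 12-month look-back may then return nothing for them, so the precision gain above is a best case.

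These points narrow the concern. They do not supply the missing window, the definitions or a rule for women without a laboratory value.

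**Conclusion.** The point holds as a gap in definition and analysis. Baseline, month-3 and month-6 values of retention and suppression are promised from charts, and no section says which records supply them. The arms are then compared without using baseline status.

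With 40 per arm, a chance baseline gap of at least 10 points arises in about 43% of trials and of at least 20 points in about 9%. This assumes that the Section 7 rates apply to this deliberately mixed sample and that care status is not balanced between arms. With complete baseline values, adjustment would lower the SD of the arm difference from about 11 points to about 10, 8 or 5 for assumed correlations of 0.5, 0.7 or 0.9. The gain shrinks if many women lack a baseline viral load. The correlations are illustrative; the documents give none.

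**What to change.** In Section 9, Medical Record Chart Abstraction:

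- Set the record window from 12 months before baseline, the protocol's own past-year period, through month 6.
- Check that the signed releases cover that window.
- Add ART fill dates, or prescription dates if fills are not in the chart.
- State the source of the care status used in purposive sampling.

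In the SAP:

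- Define baseline, month-3 and month-6 retention and viral load from the chart, with an explicit category for women who have no viral load in the window.
- Report month-3 and month-6 arm differences adjusted for chart baseline status, with confidence intervals. Low power argues against relying on tests, not against showing intervals. Records dated before randomization remain valid covariates even if retrieved later.
- Show women suppressed and not suppressed at baseline separately.

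The cost is a somewhat longer abstraction per chart, with no new visits or participants. The release forms are not available here, and the SAP is written in the past tense. If data are already collected, the window is limited to what the signed releases allow, but the SAP definitions and the adjusted analysis can still be specified for the records in hand.
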